1.2.2 Overview of deferasirox film-coated tablet

Based on the chronic nature of chelation therapy and the importance of patient compliance, an improved deferasirox formulation for oral administration is being developed (company research code ICL670). The film-coated tablet (FCT) to be used in this study contains the same active substance but has been strength-adjusted to achieve comparable exposure to the currently approved dispersible tablet. The film-coated tablet (FCT) will be available in three dose strengths (90 mg, 180 mg and 360 mg) and is dosed based on body weight. The film-coated tablets can be taken with or without a light meal.

Deferasirox film-coated tablet (FCT) is already marketed in some countries like USA or Canada, as Jadenu[®].

Pharmacokinetics

Deferasirox film-coated tablets are a strength-adjusted formulation of deferasirox with higher bioavailability compared to the Exjade[®] dispersible tablet formulation. After strength-adjustment, the film-coated tablet formulation (360 mg strength) was equivalent to Exjade[®] dispersible tablets (500 mg strength) with respect to the mean area under the plasma concentration time curve (AUC) under fasting conditions [74]. The C_{max} was increased by 30% (90% CI: 20.3% - 40.0%); however a clinical exposure/response analysis has revealed no evidence of clinically relevant effects of such an increase.

Absorption

Deferasirox (dispersible tablet formulation) is absorbed following oral administration with a median time to maximum plasma concentration (t_{max}) of about 1.5 to 4 hours. The absolute bioavailability (AUC) of deferasirox (dispersible tablet formulation) was about 70% compared to an intravenous dose. The absolute bioavailability of the film-coated tablet formulation has not been determined. Bioavailability of deferasirox film-coated tablets was 36% greater than that with Exjade[®] dispersible tablets.

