4.1 Description of study design

This is an open-label, multicenter, single arm, phase II study aimed at collecting data on preference for iron chelation therapy in patients with transfusion-dependent thalassemia (TDT) or non-transfusion-dependent thalassemia (NTDT) throughout a 48 week treatment period.

It is a pre-requisite for the patient to provide written consent for participation in this study. This must be in place prior to performing any study-related procedures or assessments, including those described at the screening visit (please refer to [Table 7-1](#) and [Table 7-2](#)

Patients will undergo up to 4 weeks of screening and if deemed eligible, will receive deferasirox dispersible tablet (DT) formulation for 24 weeks. At the completion of 24 weeks patients will be transitioned on Week 25 to an equivalent dose of the deferasirox film coated tablet (FCT) formulation and continue treatment until Week 48 (EOT of Core Phase).

Patients can then continue deferasirox FCT formulation as per the judgment of the investigator, through an extension phase for a maximum of 12 months from the last dose of deferasirox FCT received at the end of period 2 in the Core Phase.

If one of the end of study criterion is met at any time during the study, the patient must discontinue from the study and should complete the Study Evaluation Completion (SEC - visit number 777). Please refer to [Section 4.4](#) .

Patients must be followed up for 30 days after the last dose of study drug for safety evaluation (safety follow up visit).

- Core Phase:
 - Screening phase which lasts for a maximum of 4 weeks to determine patient eligibility followed by
 - Baseline visit (day 1)
 - Period 1: deferasirox DT as 20-40 mg/kg/day dose regimen of dispersible tablet formulation for 24 weeks followed by
 - Period 2: deferasirox FCT as 14-28 mg/kg/day dose regimen of film- coated tablet for 24 weeks.
- Extension Phase:

Deferasirox FCT as 14-28 mg/kg/day dose regimen of film-coated tablet.
- PRO Validation Sub-study:
 - Patients in Egypt and Thailand may participate in this optional sub-study [sub-study protocol will only be submitted in the participating countries]

[figure not shown]
Participation in the extension phase is optional. Please refer to [Section 4.4](#) for EOS criteria.

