During the regular study visits, the investigator or pharmacist will dispense to the patient or the patient's legal representative, an appropriate number of deferasirox tablets depending on the patients calculated dose. The number of tablets of each strength dispensed will be recorded in the Subject IMP dispensing and accountability log. Each time the deferasirox study drug is dispensed to the patient and/or legal patient's representative, the investigator will provide detailed instructions on how to prepare and administer the dose. Patients or the patient's legal representative will be instructed to take/administer the assigned amount of study drug and will be obliged to return all unused study medication every 4 weeks. Study medication returned by the patient or the patient's legal representative will be counted and unused study medication will be recorded by the investigator or pharmacist involved in the study. Drug accountability will be verified by the field monitor during site visits and at the completion of the trial.

Medication labels will comply with the legal requirements of the countries where the study is implemented and be printed in the local language. They will supply no information about the patient. Only the patient identifier will be entered on the medication label by the investigator or pharmacist before the corresponding medication is handed out to the patient. The storage conditions for study drug will be described on the medication label.

Patients on deferasirox DT period will take the deferasirox DT every day (not later than 12:00 PM) on an empty stomach, at least 30 minutes before the next meal. The patient will disperse the required number of deferasirox DT in a glass of water, apple juice or orange juice. Gentle stirring should be applied and continued until the tablets are fully disintegrated, which takes approximately 1 to 3 minutes. Immediately, after full disintegration of the tablets, the entire content of the glass should be swallowed.

Patients on deferasirox FCT will swallow the required number of deferasirox FCT every day (not later than 12:00 PM) with or without a light meal. For patients with difficulties in swallowing Deferasirox FCT, it is allowed to crush the film-coated tablets. They should be administered by sprinkling the full dose on soft food like yogurt or apple sauce (apple puree).

All patients should take their deferasirox dose (DT or FCT) before 12:00 PM (noon).

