Dose adjustments based on safety are allowed at any time point in the study and will be in increments of 5-10 mg/kg/day for deferasirox DT or 3.5-7 mg/kg/day for deferasirox FCT. Dose adjustments based on efficacy are permitted. For ICT naïve patients at study entry dose adjustments are allowed after 4 weeks of study treatment based on serum ferritin levels and investigator's judgement. For ICT pre-treated patients, the dose of deferasirox should be adjusted if necessary every 3 months based on the trends in serum ferritin and investigator's judgement. For more details please refer to [Table 6.2](#) – Dose of study drug based on serum ferritin level.

Table 6-2 Dose and treatment schedule

Study treatments	Pharmaceutical form and route of administration	Starting Dose* (weeks 1-4)	Dose adjustment (after week 4)	Max dose	Frequency and/or Regimen
Deferasirox DT – TDT patients	Dispersible tablets, p.o.	20 mg/kg/day	+ 5 - 10 mg/kg/day	40 mg/kg/day	Once daily
Deferasirox DT – NTD patients	Dispersible tablets, p.o.	10 mg/kg/day	+ 5 - 10 mg/kg/day	20 mg/kg/day	Once daily
Deferasirox FCT – TDT patients	Film-coated tablets, p.o.	14mg/kg/day	+ 3.5 - 7 mg/kg/day	28 mg/kg/day	Once daily
Deferasirox FCT – NTD patients	Film-coated tablets, p.o.	7 mg/kg/day	+ 3.5 - 7 mg/kg/day	14 mg/kg/day	Once daily

*Iron chelation naïve patients. All iron chelation pre-treated patients see [Section 6.1.1](#) and [Appendix 14.2](#) for guidance.

Table 6-3 Daily dose of study drug based on serum ferritin level

Dose Regimen of Drug for TDT patients	Serum ferritin level
20 mg/Kg Deferasirox DT 14 mg/Kg Deferasirox FCT	1000-1500 ng/ml
30 mg/Kg Deferasirox DT 21 mg/Kg Deferasirox FCT	>1500-2000 ng/ml
40 mg/Kg Deferasirox DT 28 mg/Kg Deferasirox FCT	>2000 ng/ml
Dose Regimen of Drug for NTD patients	Serum ferritin level
5 mg/Kg Deferasirox DT 3.5 mg/Kg Deferasirox FCT	300-799 ng/ml
10 mg/Kg Deferasirox DT	800-2000 ng/ml

Dose Regimen of Drug for TDT patients	Serum ferritin level
7 mg/Kg Deferasirox FCT	
20 mg/Kg Deferasirox DT 14 mg/Kg Deferasirox FCT	>2000 – 4000 ng/ml
30mg/Kg Deferasirox DT 21mg/Kg Deferasirox FCT	>4000ng/mL

Serum ferritin level will be measured monthly to evaluate the study drug response

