6.2.1.1 Change in patient's weight

The dose of study medication will be adapted using the Dosing Table (provided in Appendix 14.1) during the study in case the change (increase or decrease) in body weight exceeds 10% of the body weight compared to Visit 2 or the last dose adjustment due to a change in the patient's body weight.

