6.2.1.3 Changes in Serum Ferritin

Serum ferritin should be monitored monthly during the study as stated in the Visit Evaluation Schedule [Table 7-1](#) and [Table 7-2](#).

For ICT pre-treated patients, the dose of deferasirox DT should be adjusted if necessary every 3 months based on the trends in serum ferritin and investigator's judgement. [Table 6.2](#) provides additional guidance on suggested doses.

Dose adjustments should be made in steps of 5-10 mg/kg/day for deferasirox DT and of 3.5-7 mg/kg/day for deferasirox FCT and are to be tailored to the individual patient's response and therapeutic goals (maintenance or reduction of iron burden).

For TDT patients not adequately controlled with:

- Deferasirox DT doses of 30 mg/kg/day, doses of up to 40 mg/kg/day may be considered. Doses above 40 mg/kg/day are not permitted.
- Deferasirox FCT doses of 21 mg/kg/day, doses of up to 28 mg/kg/day may be considered. Doses above 28 mg/kg/day are not permitted.

For NTDT patients not adequately controlled with:

- Deferasirox DT doses of 15 mg/kg/day, doses of up to 20 mg/kg/day may be considered. Doses above 20 mg/kg/day are not permitted.
- Deferasirox FCT doses of 10.5 mg/kg/day, doses of up to 14 mg/kg/day may be considered. Doses above 14 mg/kg/day are not permitted.

In patients whose serum ferritin level has reached the target (usually between 500 and 1000 ng/mL for TDT patients or between 300-800 ng/mL for NTDT patients), dose reductions in steps of 5-10 mg/kg/day for deferasirox DT and of 3.5-7 mg/kg/day for deferasirox FCT should be considered to maintain serum ferritin levels within the target range.

If serum ferritin falls below 500 ng/mL for TDT patients and 300 ng/mL for NTDT patients, an interruption of study treatment should be considered until serum ferritin rises above 500 ng/mL or 300 ng/mL respectively.

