14.1 Dosing tables (Deferasirox DT, Deferasirox FCT)

To guide the investigator and/or pharmacist on the number of deferasirox DT or FCT tablets of a given strength to prescribe to a given patient, taking into account the patient's body weight and protocol specified dosing scheme described above, a table is provided below. Where the calculated dose cannot be constituted by the available tablet strengths, the closest dose is applied. Examples illustrating this approach are provided here below:

- For a patient whose body weight is 46 kg, and whose planned deferasirox DT dose is 20 mg/kg/day, the calculated deferasirox DT daily dose would be 920 mg. So taking into account the available strengths of 125, 250 & 500 mg deferasirox DT tablets, the patient should receive the closest daily dose of 875 mg which can be easily constituted by taking 1 x 125 mg + 1 x 250 mg + 1 x 500 mg deferasirox DT tablets = 3 tablets.
- For a patient whose body weight is 46 kg, and whose planned deferasirox FCT dose is 14 mg/kg/day, the calculated deferasirox FCT daily dose would be 644 mg. So taking into account the available strengths of 90, 180 & 360 mg deferasirox FCT tablets, the patient should receive the closest daily dose of 630 mg which can be easily constituted by taking 1 x 90 mg + 1 x 180 mg + 1 x 360 mg deferasirox FCT tablets = 3 tablets.

The dosing tables below have been constructed with cut-offs for lower and upper body weights being 20 and 143 kg respectively depending on the dose administered. This is taking into account that the study will enroll male or female patients ≥ 2 years.

Table 14-1 Deferasirox DT dosing table for 5 mg/kg/day

Pt Weight in kg	Closest Dose	125 mg	250 mg	500 mg
10 – 19.9	Please consult the Novartis Medical Lead for advice			
20 – 37.5	125	1	0	0
37.6 - 62.5	250	0	1	0
62.5 - 87.5	375	3	0	0
87.6 - 112.5	500	0	0	1
112.6 - 137.5	625	1	0	1

Table 14-2 Deferasirox DT dosing table for 10 mg/kg/day

Pt Weight in kg	Closest Dose	125 mg	250 mg	500 mg
10 – 19.9	125	1	0	0
20 – 31.3	250	0	1	0
31.4 – 43.8	375	3	0	0
43.9 – 56.3	500	0	0	1
56.4 – 68.8	625	1	0	1
68.9 – 81.3	750	0	1	1
81.4 – 93.8	875	3	0	1

Pt Weight in kg	Closest Dose	125 mg	250 mg	500 mg
93.9 – 106.3	1000	0	0	2
106.4 – 118.8	1125	1	0	2

Table 14-3 Deferasirox DT dosing table for 15 mg/kg/day

Pt Weight in Kg	Closest Dose	125 mg	250 mg	500 mg
10 – 13.9	125	1	0	0
14 - 20.8	250	0	1	0
20.9 – 29.2	375	3	0	0
29.3 – 37.5	500	0	0	1
37.6 – 45.8	625	1	0	1
45.9 – 54.2	750	0	1	1

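### Appendix 14.1: three DT rows list tablets that miss the printed dose by −50%, −40% and +33%, and Tables 14-13 and 14-7 depart widely from the closest-dose rule for small children

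*Protocol*

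**What the plan says.** Protocol Appendix 14.1 guides investigators and pharmacists on how many tablets of each strength to give at each weight and dose level. Its rule is "Where the calculated dose cannot be constituted by the available tablet strengths, the closest dose is applied". DT comes as 125, 250 and 500 mg, so every multiple of 125 mg can be made. FCT comes as 90, 180 and 360 mg, so every multiple of 90 mg can be made.

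Section 6.2.1.1 relies on these tables when weight changes: "The dose of study medication will be adapted using the Dosing Table". Section 4.1 has patients "transitioned on Week 25 to an equivalent dose of the deferasirox film coated tablet", and Section 1.2.2 gives the conversion: after strength adjustment the "film-coated tablet formulation (360 mg strength) was equivalent to" the 500 mg DT on AUC. Table 6-3 assigns 30 and 40 mg/kg DT by ferritin level; the top TDT row reads "40 mg/Kg Deferasirox DT 28 mg/Kg Deferasirox FCT".

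The introduction to the tables describes "cut-offs for lower and upper body weights being 20 and 143 kg respectively", although rows now start at 10 kg.

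**The concern.** A dosing table has two jobs: to print the right dose, and to list tablets that make it. Three DT rows fail the second. The low-weight rows of Tables 14-13 and 14-7 fail the first.

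The −50% and −40% tablet counts sit at 40 and 30 mg/kg, levels given to patients with high ferritin. The rounding failures are at 17.5 mg/kg FCT and 35 mg/kg DT, in children up to about 23 kg. Patients are eligible from age 2, and Amendment 1 extended the tables down to 10 kg. At stake are under- or over-dosing of an individual child, an intended increase that turns into a decrease, and a Week 25 change of formulation that is also a change of dose.

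**Working it through.** **The plan's own examples.** At 46 kg and 20 mg/kg DT: 46 × 20 = 920 mg, nearest multiple of 125 is 875. At 46 kg and 14 mg/kg FCT: 46 × 14 = 644 mg, nearest multiple of 90 is 630. Both match the appendix, so the rule is read as intended.

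**Tablet sums.** Total = 125a + 250b + 500c.

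| Row | Printed dose | Tablets 125/250/500 | Sum | Error | Actual mg/kg |
|---|---|---|---|---|---|
| Table 14-8 (40 mg/kg), 23.5-26.6 kg | 1000 | 0/0/1 | 500 | −50% | 18.8-21.3 |
| Table 14-6 (30 mg/kg), 39.7-43.8 kg | 1250 | 0/1/1 | 750 | −40% | 17.1-18.9 |
| Table 14-5 (25 mg/kg), 27.6-32.5 kg | 750 | 0/2/1 | 1000 | +33% | 30.8-36.2 |

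Neighbouring rows show what was meant. In Table 14-6, 1125 mg is 1/0/2 and 1375 mg is 3/0/2, so 1250 mg should be 0/1/2.

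**Closest dose.** The weight at which the next dose becomes closest is the midpoint of the two doses divided by the planned mg/kg.

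- Table 14-13 (FCT 17.5 mg/kg) prints 180 mg for 10-17.9 kg, then 360 mg. The 180/270 limit is 225/17.5 = 12.86 kg and the 270/360 limit is 315/17.5 = 18.0 kg. So 270 mg is closest at 12.9-17.9 kg. The printed 180 mg is 180/225.75 − 1 = −20% at 12.9 kg and 180/313.25 − 1 = −43% at 17.9 kg, where 270 mg would be −14%.
- Table 14-7 (DT 35 mg/kg) prints 375 mg for 10-13.9 kg, 500 mg for 14.0-19.9 kg and 875 mg for 20.0-26.5 kg. The limits are 437.5/35 = 12.5, 562.5/35 = 16.07, 687.5/35 = 19.64 and 812.5/35 = 23.21 kg. The printed dose is not closest at:
  - 12.6-13.9 kg: −15% to −23%; closest 500 mg
  - 16.1-19.9 kg: −11% to −28%; closest 625 mg, or 750 mg from 19.7 kg
  - 20.0-23.2 kg: +25% to +8%; closest 750 mg

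**Steps up that lower the dose.** Closest-dose rounding at a fixed weight can never reduce the dose when the mg/kg level rises. The printed tables do so three times:

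- FCT 14 to 17.5 mg/kg at 16.0-17.9 kg: 270 to 180 mg
- DT 30 to 35 mg/kg at 19.0-19.9 kg: 625 to 500 mg
- DT 35 to 40 mg/kg at 20.0-20.3 kg: 875 to 750 mg

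**Week 25 change.** Ratio = FCT dose / (0.72 × DT dose), with 0.72 = 360/500, at the 100 weights from 10.0 to 19.9 kg in 0.1 kg steps.

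- DT 25 to FCT 17.5: 180/(0.72 × 375) = 67% at 14.0-16.9 kg (30 weights) and 180/(0.72 × 500) = 50% at 17.0-17.9 kg (10 weights). That is 40 of 100; rounding each table separately to the closest dose would leave 8.
- DT 35 to FCT 24.5: 360/(0.72 × 375) = 133% at 12.0-13.9 kg (20 weights) and 450/(0.72 × 500) = 125% at 16.0-19.9 kg (40 weights). That is 60 of 100, against 11.
- The 10/7, 15/10.5 and 20/14 pairs match at all 100 weights.

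**The case against.** **The dose is calculated by the physician.** The printed total is right in all three tablet rows, and Section 6.1.1 has sites dispense "an appropriate number of deferasirox tablets depending on the patients calculated dose". So the tablet-count errors do harm only where someone follows the tablet columns. That stands as a limit on likelihood. But the columns are what the appendix is for, and in Tables 14-13 and 14-7 the printed total is itself the error.

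**Levels and data quality.** Table 6-3 assigns neither 25/17.5 nor 35/24.5 mg/kg; these arise through 5 mg/kg steps or deferoxamine conversion. This also limits reach. A misread cell in the PDF cannot be excluded, but all five fields of each of the three tablet rows are intact.

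A reader might infer more than the documents support:

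- *Table 14-7 breaches the maximum dose.* At 20.0-21.8 kg, 875 mg is 43.8-40.1 mg/kg, and Section 6.2.1.3 says "Doses above 40 mg/kg/day are not permitted". That limit is best read as applying to the dose level. Table 14-8, at the permitted 40 mg/kg level, itself prints 875 mg at 20.4-21.8 kg through rounding.
- *Every departure from closest dose is an error.* Over DT 10.0-26.5 kg and FCT 10.0-19.9 kg, 284 of 1862 table weights are not the closest dose. At 140 of them the printed dose is at least 10 percentage points further from plan than the closest dose, and 104 of those are in Tables 14-7 (60) and 14-13 (44). Narrow departures elsewhere, notably in the 10/7, 15/10.5 and 20/14 tables, may be deliberate pairing of DT and FCT bands.
- *All tables should simply be regenerated.* Uncapped, this would raise Table 14-8 at 11.0-11.9 kg from 375 to 500 mg, or 45.5-42.0 mg/kg at a 40 mg/kg maximum.
- *The 15% variance in Section 2.3 is the test.* Exact closest-dose rounding still exceeds 15% at 353 of the 1862 weights, so it does not separate error from rounding.

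**Conclusion.** The concern holds for the three DT tablet rows (−50%, −40%, +33%) and for the low-weight rows of Tables 14-13 (51 weights at 0.1 kg steps) and 14-7 (86 weights). The three dose reversals and the excess of non-equivalent Week 25 changes at 25/17.5 and 35/24.5 come mainly from those two tables. Nothing elsewhere in the protocol corrects these rows. It should be fixed, for patient safety.

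This rests on the rows being read correctly from the PDF, on the appendix's own rounding rule and on the 360/500 mg equivalence. The counts are of table weights, not patients; the documents do not show how many patients fall in these bands. The errors are no ground for doubting the primary McNemar test of preference, which does not use these doses.

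**What to change.** 1. Set tablet counts (125/250/500 mg) to 0/0/2 in the Table 14-8 row, 0/1/2 in Table 14-6 and 0/1/1 in Table 14-5.
2. Table 14-13: 180 mg at 10.0-12.8 kg and 270 mg at 12.9-17.9 kg.
3. Table 14-7: 375 mg at 10.0-12.5 kg, 500 at 12.6-16.0, 625 at 16.1-19.6, 750 at 19.7-23.2 and 875 at 23.3-26.5.
4. Check all tables by program for tablet sums, dose reversals and DT/FCT equivalence. Do not raise any row at the maximum level (Tables 14-8 and 14-16) further above 40 mg/kg DT or 28 mg/kg FCT. Keep shared band limits where DT and FCT already match. The equivalence check is needed even after step 2. Against the present Table 14-5, the corrected Table 14-13 gives 270/(0.72 × 250) = 150% at 12.9-13.9 kg and 270/(0.72 × 500) = 75% at 17.0-17.9 kg, 21 weights in all, so the limits of those two tables should be brought together. Table 14-15 needs the same comparison with the corrected Table 14-7.
5. Fill the missing bands (Table 14-16 between 19.9 and 21 kg, Table 14-15 between 63 and 65 kg). Correct the limits printed as 45.4-45.3 kg (Table 14-8) and 108.7-11.2 kg (Table 14-7), the overlap at 62.5 kg in Table 14-1, and the 20 kg cut-off text.

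The cost is a short program check and a protocol amendment. Section 12.1 requires ethics approval, and health-authority approval where applicable, but lets changes required for patient safety take effect before ethics approval.

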7.3.1 Preference Questionnaire

The preference questionnaire is a four item questionnaire. There are four separate versions depending on the week(s) that the questionnaire is administered.

For week 48 (primary endpoint) the first item asks the patients (or parents of young patients from 2 to 9 years old) which medicine they are currently taking with the response options: "Tablet to dissolve in liquid", "Film coated tablet ", "Sprinkle powder on food" and "I don't know". The second item asks which of the medicines did the patient "Like best" with the same response options as that of the first item. Finally, the third item asks the patient why he/she preferred the medicine they chose.

For week 28 the first item asks patients to choose from the following medicines: “Tablet to dissolve in liquid”, “Film coated tablet (taken once a day)”, “Tablet (taken 3 times a day)”, “Sprinkle powder on food”, “Injection” and “I don’t know”. The second items remain the same asking which medicine the patients like the best (out of the above response options). Similarly the third item remains the same.

For weeks 4 and 24 the first item asks patients to choose from the following medicines: “Tablet to dissolve in liquid”, “Tablet (taken 3 times a day)”, “Injection” and “I don’t know”. The second items remain the same asking which medicine the patients like the best (out of the above response options). Similarly the third item remains the same.

The following preference attributes are provided:

- Taste
- Aftertaste (taste left in your mouth after you swallow)
- Convenience (it’s not a problem to take your medicine - administration)
- Number of pills
- No/Less side effects
- Can correctly prepare the medicine
- Easier to remember to take the medicine
- Number of times you have to take the medicine
- No/Less pain on the injection site
- Gain my personal time with family and friends
- Other _____

The questionnaire is administered at week 4, week 24, week 28 and week 48. No total score is calculated on the preference questionnaire. Each item will be scored as the proportion of patients who select each response option.

7.3.2 mSICT – patients greater or equal to 10 years old

The Modified SICT (mSICT) questionnaire consists of 15 items that represent 3 domains; Adherence, Preference and Concerns.

The adherence domain consists of 7 items, 6 of which are measured using a 5 point response scale.

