54.3 – 62.5	875	3	0	1
62.6 – 70.8	1000	0	0	2
70.9 – 79.2	1125	1	0	2
79.3 – 87.5	1250	0	1	2
87.6 – 95.8	1375	3	0	2
95.9 – 104.2	1500	0	0	3
104.3 – 112.5	1625	1	0	3
112.6 – 120.8	1750	0	1	3

Table 14-4 Deferasirox DT dosing table for 20 mg/kg/day

Pt Weight in Kg	Closest dose	125 mg	250 mg	500 mg
10 – 15.9	250	0	1	0
16.0 – 21.9	375	3	0	0
22.0 – 28.1	500	0	0	1
28.2 – 34.4	625	1	0	1
34.5 – 40.6	750	0	1	1
40.7 – 46.9	875	3	0	1
47.0 – 53.1	1000	0	0	2
53.2 – 59.4	1125	1	0	2
59.5 – 65.6	1250	0	1	2
65.7 – 71.9	1375	3	0	2
72.0 – 78.1	1500	0	0	3
78.2 – 84.4	1625	1	0	3
84.5 – 90.6	1750	0	1	3
90.7 – 96.9	1875	3	0	3
97.0 – 103.1	2000	0	0	4
103.2 – 109.4	2125	1	0	4

Pt Weight in Kg	Closest dose	125 mg	250 mg	500 mg
109.5 – 115.6	2250	0	1	4
115.7 – 121.9	2375	3	0	4

Table 14-5 Deferasirox DT dosing table for 25 mg/kg/day

Pt Weight in Kg	Closest dose	125 mg	250 mg	500 mg
10 – 13.9	250	0	1	0
14.0 – 16.9	375	3	0	0
17.0 – 22.5	500	0	0	1
22.6 – 27.5	625	1	0	1
27.6 – 32.5	750	0	2	1
32.6 – 37.5	875	3	0	1
37.6 – 42.5	1000	0	0	2
42.6 – 47.5	1125	1	0	2
47.6 – 52.5	1250	0	1	2
52.6 – 57.5	1375	3	0	2
57.6 – 62.5	1500	0	0	3
62.6 – 67.5	1625	1	0	3
67.6 – 72.5	1750	0	1	3
72.6 – 77.5	1875	3	0	3
77.6 – 82.5	2000	0	0	4
82.6 – 87.5	2125	1	0	4
87.6 – 92.5	2250	0	1	4
92.6 – 97.5	2375	3	0	4
97.6 – 102.5	2500	0	0	5
102.6 – 107.5	2625	1	0	5
107.6 – 112.5	2750	0	1	5
112.6 – 117.5	2875	3	0	5
117.6 – 122.5	3000	0	0	6

Table 14-6 Deferasirox DT dosing table for 30 mg/kg/day

Pt Weight in Kg	Closest Dose	125mg	250 mg	500 mg
10 – 14.9	375	3	0	0
15.0 – 18.9	500	0	0	1
19.0 – 22.9	625	1	0	1
23.0 – 27.1	750	0	1	1
27.2 – 31.3	875	3	0	1
31.4 – 35.4	1000	0	0	2
35.5 – 39.6	1125	1	0	2

39.7 – 43.8	1250	0	1	1
43.9 – 47.9	1375	3	0	2
48.0 – 52.1	1500	0	0	3
52.2 – 56.3	1625	1	0	3
56.4 – 60.4	1750	0	1	3
60.5 – 64.6	1875	3	0	3
64.7 – 68.8	2000	0	0	4
68.9 – 72.9	2125	1	0	4
73.0 – 77.1	2250	0	1	4
77.2 – 81.3	2375	3	0	4
81.4 – 85.4	2500	0	0	5
85.5 – 89.6	2625	1	0	5
89.7 – 93.8	2750	0	1	5
93.9 – 97.9	2875	3	0	5
98.0 – 102.1	3000	0	0	6
102.2 – 106.3	3125	1	0	6
106.4 – 110.4	3250	0	1	6
110.5 – 114.6	3375	3	0	6
114.7 – 118.8	3500	0	0	7

Table 14-7 Deferasirox DT dosing table for 35 mg/kg/day

Pt Weight in Kg	Closest Dose	125 mg	250 mg	500 mg
10 – 13.9	375	3	0	0
14.0-19.9	500	0	0	1
20.0-26.5	875	1	1	1
26.6-30.1	1000	0	0	2
30.2-33.6	1125	1	0	2
33.7-37.2	1250	0	1	2
37.3-40.8	1375	1	1	2
40.9-44.4	1500			3
44.5-47.9	1625	1		3
48.0-51.5	1750		1	3
51.6-55.1	1875	1	1	3
55.2-58.6	2000			4
58.7-62.2	2125	1		4
62.3-65.8	2250		1	4

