65.9-69.4	2375	1	1	4
69.5-72.9	2500			5
73.0-76.5	2625	1		5
76.6-80.1	2750		1	5
80.2-83.6	2875	1	1	5
83.7-87.2	3000			6
87.3-90.8	3125	1		6
90.9-94.4	3250		1	6
94.5-97.9	3375	1	1	6
98.0-101.5	3500			7
101.6-105.1	3625	1		7
105.2-108.6	3750		1	7
108.7-11.2	3875	1	1	7
112.3-115.8	4000			8
115.9-119.4	4125	1		8
119.5-122.9	4250		1	8
123.0-126.5	4375	1	1	8
126.6-130.1	4500			9
130.2-133.6	4625	1		9
133.7-137.2	4750		1	9
137.3-140.8	4875	1	1	9
140.9-144.4	5000			10

Table 14-8 Deferasirox DT dosing table for 40 mg/kg/day

Pt Weight in Kg	Closest Dose	125mg	250 mg	500 mg
10.0 – 11.9	375	3	0	0
12.0 – 13.9	500	0	0	1
14.0 – 16.9	625	1	0	1
17.0 – 20.3	750	0	1	1
20.4 – 23.4	875	1	1	1
23.5 – 26.6	1000	0	0	1
26.7 – 29.7	1125	1	0	2
29.8 – 32.8	1250	0	1	2
32.9 – 35.9	1375	1	1	2
36.0 – 39.1	1500	0	0	3
39.2 – 42.2	1625	1	0	3
42.3 – 45.3	1750	0	1	3
45.4 – 45.3	1875	1	1	3
48.5 – 51.6	2000	0	0	4
51.7 – 54.7	2125	1	0	4
54.8 – 57.8	2250	0	1	4
57.9 – 60.9	2375	1	1	4
61.0 – 64.1	2500	0	0	5
64.2 – 67.2	2625	1	0	5
67.3 – 70.3	2750	0	1	5
70.4 – 73.4	2875	1	1	5
73.5 – 76.6	3000	0	0	6
76.7 – 79.7	3125	1	0	6
79.8 – 82.8	3250	0	1	6
82.9 – 85.9	3375	1	1	6
86.0 – 89.1	3500	0	0	7
89.2 – 92.2	3625	1	0	7
92.3 – 95.3	3750	0	1	7
95.4 – 98.4	3875	1	1	7
98.5 – 101.6	4000	0	0	8
101.7 – 104.7	4125	1	0	8
104.8 – 107.8	4250	0	1	8
107.9 – 110.9	4370	1	1	8
111.0 – 114.1	4500	0	0	9

Table 14-9 Deferasirox FCT dosing table for 3.5 mg/kg/day

Pt Weight in kg	Closest Dose (mg)	90 mg	180 mg	360 mg
10 – 19.9	Please consult the Novartis Medical Lead for advice			
20 - 38	90	1		
39 - 64	180		1	
65 - 89	270	1	1	
90 - 115	360			1
116 - 141	450	1		1

Table 14-10 Deferasirox FCT dosing table for 7 mg/kg/day

Pt Weight in kg	Closest Dose (mg)	90 mg	180 mg	360 mg
10 – 19.9	90	1	0	0
20 - 32	180		1	
33 - 44	270	1	1	
45 - 57	360			1
58 - 70	450	1		1
71 - 83	540		1	1
84 - 96	630	1	1	1
97 - 109	720			2
110 - 122	810	1		2
123 - 134	900		1	2
135 - 147	990	1	1	2

Table 14-11 Deferasirox FCT dosing table for 10.5 mg/kg/day

Pt Weight in kg	Closest Dose (mg)	90 mg	180 mg	360 mg
10 – 13.9	90	1	0	0
14 - 21	180		1	
22 - 29	270	1	1	
30 - 38	360			1
39 - 46	450	1		1
47 - 55	540		1	1
56 - 64	630	1	1	1
65 - 72	720			2
73 - 81	810	1		2
82 - 89	900		1	2
90 - 98	990	1	1	2
99 - 106	1080			3

Pt Weight in kg	Closest Dose (mg)	90 mg	180 mg	360 mg
107 - 115	1170	1		3
116 - 124	1260		1	3
125 - 132	1350	1	1	3
133 - 141	1440			4

Table 14-12 Deferasirox FCT dosing table for 14 mg/kg/day

Pt Weight in kg	Closest Dose (mg)	90 mg	180 mg	360 mg

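### Appendix 14.1 gives the same DT dose two tablet compositions, so patients in some weight bands take one more DT tablet a day than the worked example implies, with no FCT counterpart

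*Protocol*

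**What the plan says.** Protocol Appendix 14.1 opens with worked examples meant to show how the tables are read. The DT example begins "For a patient whose body weight is 46 kg, and whose planned deferasirox DT dose is 20 mg/kg/day" and ends with a dose of 875 mg, "easily constituted by taking 1 x 125 mg + 1 x 250 mg + 1 x 500 mg deferasirox DT tablets = 3 tablets".

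The row for that patient in Table 14-4, titled "Deferasirox DT dosing table for 20 mg/kg/day", reads "40.7 – 46.9 875 3 0 1". The last three figures are the numbers of 125, 250 and 500 mg tablets, so the total is four. Table 14-2 (10 mg/kg/day) shows the same build at a lower dose: "31.4 – 43.8 375 3 0 0".

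Table 14-8, titled "Deferasirox DT dosing table for 40 mg/kg/day", makes 875 mg from one tablet of each strength in its 20.4-23.4 kg row, and Table 14-7 does so in its 20.0-26.5 kg row. On the FCT side, Table 14-12, "Deferasirox FCT dosing table for 14 mg/kg/day", gives a 46 kg patient 630 mg as 90 + 180 + 360, three tablets, which agrees with the FCT worked example.

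The primary endpoint is preference for FCT over DT at Week 48. Protocol 7.3.1 lists "Number of pills" among the reasons a patient can give.

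**The concern.** Sites dispense from these tables, and the appendix gives them two answers for one dose. The milligrams agree but the number of tablets does not. The difference runs one way: it adds a tablet during the DT period and never during the FCT period.

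In most trials this would be editorial. Here the patient is asked which formulation they liked best and why, in a single-arm design with a fixed DT-then-FCT order. The design has no means of separating a tablet that comes from how a table was composed from one that belongs to the formulation. The planned summaries of pills received and of preference reasons would carry the difference without showing where it came from.

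**Working it through.** **1. The plan's own example.** 46 kg x 20 mg/kg = 920 mg. The distance to 875 is 45 and to 1000 is 80, so 875 mg is the closest dose. Example: 125 + 250 + 500 = 875, three tablets. Table 14-4: 3 x 125 + 500 = 875, four tablets. The dose agrees; the count differs by one.

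**2. Row count.** Take each DT row whose dose leaves 375 after whole 500 mg tablets are removed, and see how the 375 is built.

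| Table | DT mg/kg/day | Dosed rows | 375 mg remainder rows | Built as 3 x 125 |
|---|---|---|---|---|
| 14-1 | 5 | 5 | 1 | 1 |
| 14-2 | 10 | 9 | 2 | 2 |
| 14-3 | 15 | 14 | 3 | 3 |
| 14-4 | 20 | 18 | 5 | 5 |
| 14-5 | 25 | 23 | 6 | 6 |
| 14-6 | 30 | 26 | 7 | 7 |
| Sum | | 95 | 24 | 24 |
| 14-7 | 35 | | 10 | 1 (lowest row) |
| 14-8 | 40 | | 9 | 1 (lowest row) |

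The Table 14-8 row printed as 4370 mg is read as 4375, which is what its tablets sum to. Each 3 x 125 row has exactly one tablet more than 125 + 250 would need. In FCT Tables 14-9 to 14-16, all 47 rows with a 270 mg remainder use 90 + 180.

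**3. Two kinds of row.** The doses 875, 1375, 1875, 2375, 2875 and 3375 mg appear with both builds. That covers 18 of the 24 rows. The other six are the plain 375 mg rows, one in each of Tables 14-1 to 14-6. All eight DT tables print 375 mg as 3 x 125, so these rows depart from the example's convention but not from one another.

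**4. Share of patients.** The documents give no weight distribution. Counting whole kilograms as equally likely:

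- 20 mg/kg, 20-80 kg: affected weights are 20-21, 41-46 and 66-71, so (2 + 6 + 6)/61 = 14/61 = 23%.
- 20 mg/kg, narrower bands: 25-40 kg 0%; 47-65 kg 0%; 40-60 kg 6/21 = 29%.
- 10 mg/kg, 20-80 kg: affected weights are 32-43, so 12/61 = 20%, all in the plain 375 mg row.
- 10 mg/kg, narrower bands: 50-80 kg 0%; 25-40 kg 9/16 = 56%.

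**5. Tablets per day, one scenario.** At 20 mg/kg DT against 14 mg/kg FCT, summed over the 61 weights: DT as printed 170/61 = 2.79; DT built as in the example (170 - 14)/61 = 2.56; FCT 154/61 = 2.52.

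**6. Compliance ratio.** It is the count consumed over the count prescribed. A patient who takes a fraction f of D days' doses has 4fD/4D = f with four tablets and 3fD/3D = f with three, provided both counts come from the same table row.

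**The case against.** The strongest reply is that this is an editorial slip with the milligram dose intact. DT is dispersed in a glass and drunk, so three or four tablets is a minor matter of handling beside taste, fasting, and dispersing versus swallowing. Tablet number is one of eleven listed reasons. Nothing in the documents quantifies an effect on preference. All of that stands.

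It also stands that row counts are not patients. Table 6-3 puts TDT patients with ferritin above 2000 ng/ml on 40 mg/kg, where Table 14-8 carries an extra tablet only in its 10-11.9 kg row. The plan already summarises pills received and preference reasons by treatment. And 132 of about 145 patients were enrolled at Amendment 1, so correcting the appendix can change little for this endpoint.

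One possible defence fails. Protocol 6.1 allows the strengths supplied to differ by country, but that does not explain the pattern, because the same six tables use the 250 mg tablet in their 250 mg remainder rows.

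A reader might infer that the extra DT tablets distort the compliance comparison. They do not, because they enter numerator and denominator alike. A reader might also infer that nearly all of DT's excess tablet burden in the study comes from the tables. The figures 2.79, 2.56 and 2.52 describe one dose pair under an assumed even weight spread, and are not a study estimate.

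**Conclusion.** The contradiction is real and systematic. It covers 24 of 24 rows with a 375 mg remainder in Tables 14-1 to 14-6, plus the lowest rows of Tables 14-7 and 14-8. In those weight bands, patients take one DT tablet a day more than the worked example implies, and the FCT tables have no matching excess. It does not apply to every DT patient. Under an even 20-80 kg spread about 23% are affected at 20 mg/kg. Across narrower bands at 10 and 20 mg/kg the share runs from 0% to 56%, and that upper end rests on the plain 375 mg row.

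Any effect on preference would favour FCT, but its size is unknown and probably small. The documents do not support saying that the Week 48 result is materially biased. Severity is minor: the case for acting is that sites dispense from these tables and the remedy costs almost nothing.

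**What to change.** The sponsor should reconcile the worked example with Tables 14-1 to 14-8 so that each printed DT dose has one tablet composition, and state whether the plain 375 mg dose follows the same rule. This review does not say which composition is right. The daily milligram doses are not in question here.

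For patients already dosed, use the tablets dispensed by strength, which Protocol 7.2.3 already sends to the Drug Accountability eCRF. Tabulate tablets per day by formulation. Describe Week 48 preference, and how often "Number of pills" was chosen, by whether the patient's DT row carried the extra tablet. Label this descriptive and add no test: the split is confounded with weight, age and dose. The latest SAP version also postdates the interim database lock, so the table would be post hoc.

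The cost is an appendix correction with any further amendment, one extra descriptive table, and possibly a small shift in the mix of 125 and 250 mg DT stock. No new data are needed.
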